### 9.2. Statistical Analysis of Safety Data

Descriptive statistics will be calculated on the safety parameters using the ITT population. The proportion of subjects with treatment-emergent adverse events will be tabulated and presented by treatment and Medical Dictionary for Regulatory Activities (MedDRA) System Organ Class. Vital signs, LSR scores and clinically relevant abnormal laboratory results will also be tabulated and presented by study medication. No inferential testing will be performed.

Data from all randomized subjects will be presented and summarized. Safety summaries by study medication group will include listings by study medication of adverse events incidences within each MedDRA System Organ Class, and changes from pre-application values in vital signs. Adverse event summaries will be presented by study medication showing the proportion of subjects experiencing adverse events, both overall and by MedDRA System Organ Class.

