## 4.6. Subject Discontinuation from the Study

Subjects will be informed that they are free to withdraw from the study at any time and for any reason.

The investigator may remove a subject from the study if, in the investigator's opinion, it is not in the best interest of the subject to continue the study. Examples of other reasons subjects may be discontinued from the study are a change in compliance with an inclusion or exclusion criterion, occurrence of AEs, occurrence of pregnancy or use of a prohibited therapy. Immediately (within 24 hours) notify the Aclaris Therapeutics, Inc. study monitor of discontinuation.

In case of premature discontinuation of study participation, efforts will be made to perform all final study day assessments. The date the subject is withdrawn from the study and the reason for discontinuation will be recorded on the subject's case report forms (CRFs). All withdrawn subjects with ongoing AEs will be followed as appropriate (Section 7.2.1).

The study may be discontinued at the discretion of Aclaris Therapeutics, Inc. Some examples of reasons for discontinuation are the occurrence of the following:

- Increased frequency, severity or duration of known AEs
- Medical, regulatory or ethical reasons affecting the continued performance of the study
- Difficulties in the recruitment of subjects.

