- 17. Discharge from the study subjects who are not eligible for randomization [Section 4.6].

- For subjects eligible for randomization the investigator or designee will perform the following procedures:
  - 1. Randomize eligible subjects (Section 5.7.4)
  - 2. Perform the initial study medication application for the target lesion Section 5.7.6
  - 3. Monitor the subject for at least 20 minutes after the Application Completion Time to detect any adverse events (Section 7.2.1)
  - 4. Have the subject perform a post-application Local Skin Reaction assessment of the symptoms for the target lesion 10 (±4) minutes after the Application Completion Time (Section 6.2.1)
  - Perform a post-application Local Skin Reaction assessment of the signs for the target lesion 20 (±4) minutes after the Application Completion Time Section 6.2.1
  - 6. Review the study instructions and restrictions with the subject (Section 5.5)
  - 7. Schedule Visit 3 for Day 8.

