## 5.7.8. Dose modification

Study medication applications will be performed at Visit 2, and if appropriate Visit 4, by the investigator or an investigational center staff member at the direction of the investigator. No study medication will be dispensed to the study subjects.

If any subject refuses to allow the initial study medication treatment or a retreatment application, the investigator must report the visit number, visit date and the reason for the refusal on the subject's Comments CRF page.

If the subject's refusal is associated with an AE, the investigator must report the event on the appropriate CRF (Section 7.2).

The subject must have the initial study medication application to the target lesion to remain in the study.

The subject does not need to be removed from the study based solely on her/his refusal to have a study medication retreatment application on the target lesion.

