## 5.10.2. Un-blinding during the study medication

Blinding is important for validity of this clinical study. However, the blind may be broken in the event of a medical emergency, in which knowledge of the study medication identity is critical to the management of the subject's course of treatment. Before breaking the blind the investigator should determine that the information is necessary (*i.e.*, that it will alter the subject's immediate course of treatment). In many cases, particularly when the emergency is clearly not study medication-related, the problem may be effectively managed by assuming that the subject is receiving an active study medication without the need for un-blinding.

If deemed necessary to break the blind for a study subject, attempt to contact the Aclaris Therapeutics, Inc. Medical Monitor (protocol page 1 and Section 7.2.2) to obtain concurrence. If it is not possible to contact the Medical Monitor beforehand, contact her/him as soon as possible after breaking the blind for a subject.

To identify a subject's study medication, locate the second panel of the tear-off label attached to the subject's Label Page CRF and follow the instructions on the label. Record the date of un-blinding, the reason for un-blinding and the initials of the investigational center staff member who performed the un-blinding on the subject's Label Page CRF.

Any subject whose blind has been broken must be discharged from the study (Section 4.6).

At the end of the study, the original Label Page CRFs will be returned to Aclaris Therapeutics with a photocopy placed in the investigator's study file. The original Label Page CRFs will be available, upon request, to the site if needed to respond to a regulatory audit.

Any event that requires the use of an eyewash kit the investigator is required to break the blind for the subject and take appropriate action (Section 7.1.1).

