#### 7.1. Definitions

#### 7.1.1. Adverse events (AE)

An AE is any untoward medical occurrence in a patient or clinical investigation subject administered a study medication(s) and which does not necessarily have a causal relationship with the study medication. An AE can therefore be any unfavorable and unintended sign or symptom associated with the use of a study medication (including an abnormal laboratory finding), whether or not related to the study medication.

Thus any new, clinically relevant worsening of an existing sign, symptom or disease, should be considered an AE.

Worsening of any of the target lesion assessments should be reported as an AE ONLY if the use of the study medication is interrupted or discontinued or if therapy is required to manage the event.

The investigator must, for any AE associated with a target lesion, question the subject in detail to determine if there are any confounding factors (*e.g.*, irritation by clothing or activity, sunburn) for any such AE.

Report any event that requires use of the eyewash kit [Section 5.7.6] as an AE for "eye irritation". For all AEs of this type:

- Contact the medical monitor (see contact information on Page 1, or in Section 7.2.2) immediately (within 24 hours)
- Unblind the study medication for the subject (Section 5.10.2)
- Arrange for the subject to be transported to the most appropriate hospital emergency room (ER) and provide the study medication identification information to the appropriate ER staff
- Follow the course of the AE
- Report the event as an SAE if appropriate (Section 7.1.2).

Every new episode or clinically relevant worsening of a chronic condition (*e.g.*, headaches, seasonal allergies, depression, and hypertension) should be reported as a separate AE, even if the condition is reported in the subject's medical history.

The investigator should, when certain, report a diagnosis rather than the signs, symptoms or clinically relevant abnormal laboratory values associated with the AE. Otherwise, signs, symptoms or abnormal laboratory values may be used to describe the AE.

Any CR abnormality discovered prior to the first study medication application should be reported as medical history, not as an AE.

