# 9. STATISTICAL ANALYSES

## 9.1. Statistical Analysis of Clinical Indices

The primary effectiveness analysis will consist of mean change from baseline to Visit 8 PLA performed using Analysis of Covariance (ANCOVA) with baseline PLA as the covariate. The analysis will be performed at each post-baseline visit with emphasis on Visit 8. Comparisons between vehicle and each active treatment group will be performed within the model using least-squares means and the common error term. The primary efficacy analyses will be based on the per protocol (PP) population, defined as all randomized subjects who completed the study with no major protocol violation.

A secondary efficacy analysis of a separate comparison between each active treatment group and the vehicle treatment group based on the proportion of subjects whose target lesion is judged to be clear on the PLA (PLA = 0) at Visit 8. A separate Cochran-Mantel-Haenszel (CMH) test stratified by Site will be used for each comparison. A secondary efficacy analysis will also be conducted using this same methodology, but based on SSA.

Secondary analyses will initially be performed on the PP population, but will also be performed on the intent-to-treat (ITT) population defined as all randomized subjects with non-missing data at baseline and at least one post-baseline visit. As a secondary analysis, the primary efficacy analysis will be performed using the ITT population. For all ITT-population analyses, missing efficacy data will be imputed from the last non-missing post-baseline visit carried forward to subsequent missing visits (LOCF).

For all analyses, two-tail alpha will be set to 0.05 with no adjustment for multiple comparisons. ANCOVAs will include Site in the model if doing so improves the sensitivity of the model for comparing treatment groups. As a sensitivity analysis, the primary efficacy analysis will also be run including Site and the Treatment-by-Site interaction. If the interaction term is associated with p < 0.10 then treatment group means for each Site will be examined individually to understand potential site differences. Sites with less than two completed blocks of subjects will be pooled with other such Sites to achieve new pooled analysis Sites that meet this criterion. Sites will

first be ranked by sample size and then pooled in that order until each new pooled analysis Site meets the two-block threshold.

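### Section 9.2 names two different safety populations (ITT and all randomized); under the ITT rule, a subject treated on Day 1 with no later visit may drop out of the safety summaries.

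*Combined protocol and SAP*

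**What the plan says.** Section 9.2 gives two bases for the safety analysis. Its first paragraph reads "Descriptive statistics will be calculated on the safety parameters using the ITT population" and goes on to tabulate treatment-emergent adverse events, vital signs, local skin reaction (LSR) scores and laboratory abnormalities. Its second paragraph reads "Data from all randomized subjects will be presented and summarized" and again promises adverse event proportions, overall and by System Organ Class.

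Section 9.1 supplies the ITT definition: "intent-to-treat (ITT) population defined as all randomized subjects with non-missing data at baseline and at least one post-baseline visit". The only other defined analysis set is the per protocol population.

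Safety data are collected on Day 1 after dosing. The Visit 2 procedures (Section 5.3.2) include "Monitor the subject for at least 20 minutes after the Application Completion Time to detect any adverse events", and LSR symptoms and signs are read about 10 and 20 minutes after the application.

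Three further provisions bear on who could be lost:

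- Section 7.1.1 instructs sites: "Report any event that requires use of the eyewash kit" as an adverse event of eye irritation, and to unblind that subject. Section 5.10.2 then states: "Any subject whose blind has been broken must be discharged from the study".
- Section 4.6 states: "In case of premature discontinuation of study participation, efforts will be made to perform all final study day assessments".
- Section 5.7.8 covers refusal of treatment: "If any subject refuses to allow the initial study medication treatment or a retreatment application", the investigator must document it. A subject must have the initial application to remain in the study.

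**The concern.** The two sentences of Section 9.2 give the same adverse event table two possible denominators and, for some subjects, two possible numerators. Two analysts could each follow the section faithfully and report different rates for the same arm. Nothing in the plan fixes the choice before the data are seen.

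The ITT definition suits an efficacy analysis that carries the last post-baseline value forward. It suits safety poorly, because a treated subject already has post-dose safety data on Day 1 and needs no later visit to contribute. The subject at risk of exclusion is one who leaves at once, and leaving at once can be a consequence of an adverse event.

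Safety on the face is a stated objective (Section 3), and its analysis is descriptive only. The tabulated results are therefore the whole of the safety evidence, and their denominators should not be open to choice.

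**Working it through.** The plan states no figure on this point, so there is none to reproduce. The check compares the definitions and then illustrates the size.

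**Step 1: compare the sets.** ITT is all randomized subjects less those without baseline data or without any post-baseline visit (Section 9.1). It is a subset of all randomized subjects, and the two coincide only if nobody is removed. Neither set is the treated population: all randomized also counts anyone who refuses the first application. That should be rare, because application follows randomization at the same visit.

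**Step 2: who can fall between the sets.** Baseline and first application are both at Visit 2. The first later visit is Visit 3, 7 (±4) days after Visit 2 (Section 5.3.3). A subject dosed at Visit 2 and never seen again has Day 1 adverse event and LSR data but no post-baseline visit, unless Day 1 post-application data are counted as one, which Section 9.1 does not say. The eyewash, unblinding and discharge sequence is one route to this outcome.

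The group could be wider. Section 9.1 does not say which data must be non-missing. If it means the PLA, the first post-baseline PLA is at Visit 4, Day 22 (Section 6.1.2), and a subject seen only through Visit 3 would be excluded too.

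**Step 3: size, as an illustration.** Inputs from the plan: about 36 randomized per arm (Section 4.1), 108 in total, with a goal of 96 completers (Synopsis). Allowed non-completers are 108 − 96 = 12, which is 12/108 = 11.1%, or 12/3 = 4 per arm.

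Let k be the subjects in one arm with a Day 1 event and no later visit, and x the other subjects in that arm with the event. All 36 are taken as treated.

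- All randomized: (x + k)/36
- ITT, if the k subjects are excluded: x/(36 − k)

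With x = 0 and Clopper-Pearson 95% intervals:

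| k (assumed) | All randomized | ITT |
|---|---|---|
| 0 | 0/36 = 0% | 0/36 = 0% |
| 1 | 1/36 = 2.8% (0.07 to 14.5%) | 0/35 = 0% (0 to 10.0%) |
| 2 | 2/36 = 5.6% (0.7 to 18.7%) | 0/34 = 0% (0 to 10.3%) |
| 4 | 4/36 = 11.1% (3.1 to 26.1%) | 0/32 = 0% (0 to 10.9%) |

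With x = 3 and k = 1, the rates are 4/36 = 11.1% and 3/35 = 8.6%.

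The row k = 4 is an extreme in which every allowed loss in the arm is such a subject.

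**The case against.** The strongest reply is that Section 9.2 already protects these subjects. Its second paragraph covers all randomized subjects and goes on to specify the adverse event summaries, so if it governs, nobody is lost. That is a fair reading but not the only one, because the first paragraph also tabulates adverse event proportions and places them on ITT.

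The route to exclusion is also narrow. The event must occur at Visit 2, no final assessment must be obtained, and the ITT sentence must prevail. An eyewash event at Visit 4 would normally follow a completed Visit 3. Related adverse events are followed to resolution or stability (Section 7.2.1), so the event would be recorded, and only its place in the tables is at risk. All of this stands, and it is why the loss is possible rather than certain. But Section 4.6 promises efforts only, and Section 9.1 does not say whether an early-termination assessment counts as a post-baseline visit.

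The illustration can be pressed too. Section 9.3 ties the 32 per arm to the per protocol definition, which also removes major protocol violators. The allowance of 4 per arm is therefore a planning figure: it is neither a forecast of early losses nor a bound on them. The documents support no particular k, and k = 1 is the reasonable illustration.

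Finally, Section 10.3 has evaluability determined before database lock. That limits late discretion over individual subjects, but it does not say which population governs the safety tables.

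**Conclusion.** The inconsistency is real and can be read directly from the text: Section 9.2 assigns safety summaries to two different populations, and no definition settles which applies. If the ITT sentence governs, a treated subject's Day 1 safety data may be omitted.

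The numerical effect is likely to be small. One affected subject in an arm of 36 turns 2.8% into 0%. The effect is nil if no such subject occurs, if an early-termination assessment counts as a post-baseline visit, or if the all-randomized sentence governs. The values of k are assumptions, and the direction of any bias between arms cannot be established from the documents. Efficacy results, power and error rates are not affected.

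This should be fixed: it concerns a stated objective, a single affected event could vanish from a table, and the correction is nearly free. Confidence is high on the inconsistency; whether any subject would in fact be lost is unknown.

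**What to change.** In Section 9.2, replace the ITT sentence with wording such as:

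*Safety analyses will use the Safety population, defined as all subjects who received at least one study medication application (including a partial one), grouped by medication received, with no post-baseline visit requirement.*

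Change the all-randomized sentence to refer to the same population; all randomized subjects can still appear in listings and in the disposition table. Use the Safety population for the adverse event, LSR (including the Day 1 post-application readings), vital sign and laboratory summaries, and show the number of subjects with data at each time point.

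The cost is one definition and one aligned sentence. No data collection, visit or sample size changes.

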#### 2. INTRODUCTION

#### 2.1. Summary

Seborrheic keratosis (SK) is one of the most common skin tumors in man. These benign epithelial skin tumors are most commonly seen in older individuals, increasing in prevalence with increasing age, and affect men and women roughly equally. While the growths may be solitary, they often occur in large numbers and typically present as well demarcated, elevated or "stuck-on" appearing papules or plaques that may vary from flesh-colored, to shades of yellow, gray, brown, or black.

Though benign, SK lesions are often cosmetically worrisome to patients, must sometimes be distinguished from other benign or malignant skin tumors and may become pruritic, irritated, bleed, and may be painful when traumatized particularly when located in areas prone to friction and trauma such as belt-lines and brassiere-strap lines.

Patients often seek treatment of SK for cosmetic reasons, particularly if they are located in a highly visible ("cosmetically sensitive") area such as the face, and especially if they are large, pigmented, if multiple lesions are present, or simply because the lesions are commonly associated with "old age". Removal may be medically indicated, however, for lesions that become irritated, pruritic, inflamed, or painful, or for lesions that the clinician feels require histologic confirmation of the diagnosis.

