# 5.3.2. Visit 2 (Day 1)

This visit must occur within 14 days after Visit 1.

Subsequent study visit dates must be scheduled based on the date of Visit 2.

This visit may not occur before the investigator reviews the Visit 1 clinical laboratory test results. For the subject to continue in the study all required clinical laboratory test results must be within the range of normal for the laboratory or, if there are any abnormal results, they must be defined as not clinically relevant (NCR) by the investigator (Section 6.2.3).

At this visit, the investigator or designee will perform the following procedures PRIOR TO RANDOMIZATION:

- 1. Query the subject in a non-directive manner about any changes in her/his health since the previous visit and report all AEs on the appropriate form [Section 7.2.1]
- 2. Query the subject about any changes in her/his concomitant therapies since the previous visit and report changes on the appropriate form (Section 4.5.2)
- 3. Confirm the subject continues to comply with all study restrictions, is eligible to continue in the study and has followed all study instructions (Section 5.5)
- 4. Confirm the subject did not use any prohibited therapies (Section 4.5.3)
- 5. Measure vital signs (Section 6.2.2)
- 6. Collect concomitant therapies information (Section 4.5.2)
- 7. Collect blood samples for clinical laboratory tests Section 6.2.3
- 8. Perform a urine pregnancy test for women of childbearing potential (WOCBP); results must be negative for the subject to be randomized [Section 6.2.4]
- 9. Confirm the location of the target lesion (Section 5.4)
- 10. AT ONE SELECTED CENTER ONLY take standardized color photographs of the target lesion (Section 6.3.2)
- 11. Have the subject perform an SSA for the target lesion (Section 6.1.1)
- 12. Have the subject perform a pre-application Local Skin Reaction assessment of the symptoms for the target lesion (Section 6.2.1)
- 13. ONLY AFTER THE SUBJECT COMPLETES THE SSA perform a PLA for the target lesion; a PLA grade of ≥2 is required for the target lesion for the subject to be randomized [Section 6.1.2]
- 14. Perform a pre-application Local Skin Reaction assessment of the signs for the target lesion (Section 6.2.1)
- 15. Measure the dimensions of the target lesion; for the target lesion the longest axis must be ≥7mm and ≤15mm and the longest dimension perpendicular to the longest axis must be ≥7mm and ≤15mm (Section 5.4)
- 16. Confirm subject is eligible for randomization (Section 5.7.4)

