## 6.2.1. Local Skin Reactions (LSR)

The LSR assessment is the investigator's assessment of the signs and the subject's assessment of the symptoms associated with irritation at the target lesion site (*i.e.*, the target lesion and the skin immediately surrounding the target lesion exposed to study medication). The investigator and subject must NOT refer to any other evaluation to assist with these assessments. This is not a comparison with the assessment at any other time point.

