#### 9.3. Sample Size

The sample size of 32 subjects per treatment group completing the study (as defined for the PP population) is based on previous data suggesting that the proportion of subjects with a clear lesion (PLA=0) at Visit 8 would be at least 0.325 for the highest active dose group with no more than 1 vehicle subject (a proportion of approximately 0.031) achieving a clear lesion at Visit 8. Under these assumptions this study would have approximately 87% power with two-tail alpha = 0.05, using the more conservative secondary efficacy endpoint. The ANCOVA analysis of the primary endpoint, mean change from baseline PLA for the PP population, is expected to be more sensitive than the above endpoint, with power greater than 90% under similar assumptions.

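### Section 9.2 plans local skin reactions only as scores by arm, so for reactions the lesion itself can produce, clearance on active drug can mask treatment-emergent findings

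*Combined protocol and SAP*

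**What the plan says.** Section 9.2 (Statistical Analysis of Safety Data) is descriptive throughout. For LSR it states: "Vital signs, LSR scores and clinically relevant abnormal laboratory results will also be tabulated and presented by study medication". The only summary it ties to a value before treatment is "changes from pre-application values in vital signs". It names no LSR shift table, count of worsened subjects or definition of a treatment-emergent reaction, although it does report adverse events as treatment-emergent.

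Section 6.2.1 defines the rated site as "the target lesion and the skin immediately surrounding the target lesion exposed to study medication". Each rating is made without reference to any other time point. The items include erythema, scaling/dryness and pruritus.

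The baseline will exist. Section 5.3.2 lists, before randomization, "Perform a pre-application Local Skin Reaction assessment of the signs for the target lesion", and the subject grades the symptoms at the same visit.

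Section 2.1 says that these lesions "may become pruritic, irritated, bleed, and may be painful when traumatized", and later gives inflammation as one reason for removal. Section 7.1.1 makes worsening of a target lesion assessment an adverse event only if study medication is interrupted or stopped, or if treatment is needed.

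**The concern.** If an untreated lesion itches or is red, that finding enters the LSR grade. Randomization balances this background before the first application, but not afterwards. Clearing a lesion can remove its own itch or redness, and clearance is expected far more often on active drug. Vehicle lesions mostly keep theirs. A raw table then sets the disease persisting on vehicle against a mixture of cleared disease and drug reactions on active.

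The raters do not subtract the background, because they are told not to compare with other time points. Only the analysis can do so. Adverse event tables are a partial backstop at best, since milder site reactions are kept out of them. Safety on the face is a stated objective and LSR is its main local measure. If the two concentrations clear at different rates, comparison of their LSR tables is affected as well.

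**Working it through.** **Inputs from the documents (Section 9.3).** "The sample size of 32 subjects per treatment group completing the study"; the clear rate at Visit 8 "would be at least 0.325 for the highest active dose group"; 0.031 on vehicle; "approximately 87% power with two-tail alpha = 0.05".

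**Assumed inputs, not in the documents.**
- *b*: share of subjects whose lesion itself produces the finding (grade above 0) before application.
- *r*: share with a drug-caused finding at Visit 8.
- Clearance removes the lesion's own finding, and uncleared lesions keep it.
- The lesion's own finding, clearance and drug reactions are independent.
- Vehicle causes no reactions.

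**Step 1: the plan's own figure.** The difference is 0.325 − 0.031 = 0.294 and the mean rate is 0.178.
- Pooled standard error: √(2 × 0.178 × 0.822 / 32) = 0.0956.
- Unpooled standard error: √[(0.325 × 0.675 + 0.031 × 0.969) / 32] = 0.0883.
- Power: Φ[(0.294 − 1.96 × 0.0956) / 0.0883] = Φ(1.21), about 88.6%.

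Fisher's exact test gives 85.2%. The stated figure of about 87% lies between the two, so the clear rates can be reused.

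**Step 2: raw rates at Visit 8, any grade above 0.**
- Vehicle: V = b × (1 − 0.031) = 0.969b.
- Active: A = 0.675b + r × (1 − 0.675b).
- For b = 30% and r = 10%: V = 0.2907 and A = 0.2025 + 0.10 × 0.7975 = 0.2823. The difference is −0.8 points before rounding the rates.

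**Step 3: when the raw comparison reverses.** A < V when r < 0.294b / (1 − 0.675b).
- b = 5%: 0.0147 / 0.96625 = 1.5%
- b = 20%: 0.0588 / 0.865 = 6.8%
- b = 30%: 0.0882 / 0.7975 = 11.1%

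**Step 4: the range, with r fixed at 10%.**

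| b | Raw vehicle | Raw active | Raw difference (points) | Reverses if r is below | New finding among all subjects, active vs vehicle |
|---|---|---|---|---|---|
| 0% | 0% | 10.0% | +10.0 | never | 10.0% vs 0% |
| 5% | 4.8% | 13.0% | +8.2 | 1.5% | 9.5% vs 0% |
| 20% | 19.4% | 22.2% | +2.8 | 6.8% | 8.0% vs 0% |
| 30% | 29.1% | 28.2% | −0.8 | 11.1% | 7.0% vs 0% |

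The last column is r × (1 − b): grade 0 before application and above 0 at Visit 8. Among subjects at grade 0 before application it is 10% against 0% in every row.

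**Step 5: would mean change from baseline help?** No. The baseline is b in both arms in expectation, so (A − b) − (V − b) = A − V. The difference at b = 30% is still −0.8 points. What helps is classifying each subject against his or her own starting grade.

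**The case against.** The strongest case against has four parts.

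1. **The LSR definition.** Section 6.2.1 concerns findings associated with irritation, while lesion surface and thickness are graded separately on the PLA and SSA. An investigator may therefore not score lesion texture as scaling. This stands for scaling: the nearest support is the word *rough* at the severe SSA grade, and the documents do not say that untreated lesions scale. It does not dispose of pruritus or erythema, because Section 2.1 describes itch, irritation and inflammation.

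2. **The inputs are assumed.** No document gives a pre-treatment prevalence or a drug-caused rate at Visit 8. Section 2.1 says only that lesions may become symptomatic and mentions friction sites away from the face. Enrolled lesions are stable, typical and at most 2 mm thick. Every arm is rubbed firmly with alcohol and solution, so a vehicle rate of zero is a simplification. All of this stands. At b = 5% the reversal threshold is about half a subject in 32 (0.015 × 32).

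3. **Nothing is lost.** The list of summaries in Section 9.2 is not exclusive, grades before application could appear in the tables, and subject-level data are kept. A reader might infer that the within-subject information is unrecoverable or that baseline grades are excluded; the documents support neither. The gap is in what is prespecified, and naming the tables now avoids choosing them after unblinding.

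4. **The raw comparison is valid for what it measures.** Net site condition by arm is a legitimate randomized contrast, and no test or decision rests on it. That is true, but it does not separate findings that come from the lesion from those that emerge on treatment.

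A reader might also infer that the whole LSR profile is compromised. It is not. The documents give no basis for saying that an untreated lesion produces vesicles, erosion, ulceration, atrophy or scarring, and clearance cannot act on the 10- and 20-minute readings at Visit 2.

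**Conclusion.** The point holds in a limited form. For pruritus and erythema, and possibly scaling, at visits after lesions have cleared, scores tabulated by arm can understate or mask treatment-emergent reactions relative to vehicle. Section 9.2 names no summary that would show this.

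The size cannot be stated from the documents. It ranges from nothing at b = 0, through a 10% drug-caused rate appearing as 8.2 points (b = 5%) or 2.8 points (b = 20%), to a reversal of 0.8 points (b = 30%). These figures rest on independence, on clearance removing the lesion's own finding, on no vehicle-caused reactions, and on clear rates that the plan gives for Visit 8 and the highest dose only. It would go too far to conclude that harm will be reversed in this trial: that depends on a prevalence nobody has documented. The improvement is worth making because it costs little and uses grades already collected.

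**What to change.** In Section 9.2, keep the raw LSR tables and add, by item, visit and study medication:

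- a shift table from the Visit 2 grade before application;
- the proportion of subjects with a new or worsened grade relative to that baseline, with the same proportion among subjects at grade 0 before application.

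Mean change from baseline alone should not be used for this purpose (Step 5).

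The cost is a few more descriptive tables and some wording in Section 9.2. No data collection or inferential test is added, and no dosing or clinical rule is affected. One limit should be stated with the tables: they miss a drug reaction of the same or a lower grade in a subject whose own lesion finding has gone with clearance.
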